## 7 CONCOMITANT AND SUPPORTIVE THERAPY

### 7.1 Concomitant Medications

Other than the study drug, any treatments (including prescription and non-prescription drugs, health foods, herbal remedies, self-prescribed drugs, street drug, tobacco products, or alcohol) taken by a subject from the screening period through the 4-Week End of Treatment Follow-Up are considered concomitant medications. Information regarding all concomitant medications will be collected and documented in the concomitant medication page of the eCRF.

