### 11.10 Concomitant Medication Use

Concomitant medications will be coded by means of the World Health Organization Drug Dictionary into Anatomical-Therapeutic-Chemical classification codes. The type and timing (between each visit) of use of specific concomitant medications will be listed and summarized.

The frequency, timing (between each visit), type, and amount of any other therapies for aniridia will be considered with special interest.

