7.5.5 Physical Examinations and Other Parameters

Height, weight, physical examination, ophthalmoscopy, slit-lamp examination, and visual fields will be summarized by visit using descriptive statistics over the course of the study. Medications taken prior to entering the study and started while on study (i.e., concomitant) will be summarized to Week 48, from Week 48 to Week 148, and through end of treatment, including sub-study.

7.6

[REDACTED]

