10.2.2.2 Incomplete Stop Date

The following rules will be applied to impute the missing numerical fields. If the date of the last dose of double-blind study drug is missing, replace it with the last visit date or data cut-off date if the subject is on-going. If the imputed stop date is before the start date (imputed or non-imputed start date), then the imputed stop date will be equal to the start date.

Missing day and month

- If the year of the incomplete stop date is the same as the year of the date of the last dose of double-blind study drug, then the day and month of the date of the last dose of double-blind study drug will be assigned to the missing fields.
- If the year of the incomplete stop date is prior to the year of the date of the last dose of double-blind study drug, then December 31 will be assigned to the missing fields.
- If the year of the incomplete stop date is after the year of the date of the last dose of double-blind study drug, then January 1 will be assigned to the missing fields.

Missing month only

- The day will be treated as missing and both month and day will be replaced according to the above procedure.

Missing day only

- If the month and year of the incomplete stop date are the same as the month and year of the date of the last dose of double-blind study drug, then the day of the date of the last dose of double-blind study drug will be assigned to the missing day.
- If either the year is before the year of the date of the last dose of double-blind study drug or if both years are the same, but the month is before the month of the date of the last dose of double-blind study drug, then the last day of the month will be assigned to the missing day.
- If either the year is after the year of the date of the last dose of double-blind study drug or if both years are the same, but the month is after the month of the date of the last dose of double-blind study drug, then the first day of the month will be assigned to the missing day.

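### SAP 10.2.2.2 ties partial medication stop dates to the last masked dose, so open-label medication use can be shortened, misplaced or, in some cases, lost

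*SAP*

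**What the plan says.** SAP 10.2.2 imputes incomplete start and stop dates for prior and concomitant medications, start date first when both are incomplete. SAP 10.2.2.2 then compares the known part of the stop date with the last double-blind dose:

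- Year only, same year as that dose: "then the day and month of the date of the last dose of double-blind study drug will be assigned to the missing fields".
- Year only, later than "the year of the date of the last dose of double-blind study drug, then January 1 will be assigned to the missing fields".
- Day missing, same month as that dose: the stop is set to the day of that dose.
- Day missing, later month or year: "then the first day of the month will be assigned to the missing day".
- Stops before the anchor go the other way, to December 31 or the last day of the month.
- If the result precedes the start date, "then the imputed stop date will be equal to the start date".

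Protocol 6.2.1 puts the last Stage 1 dose on the evening before the Week 48 visit, so the anchor is the Stage 1/Stage 2 boundary.

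On definition, Protocol 7.1 says that treatments "taken by a subject from the screening period through the 4-Week End of Treatment Follow-Up are considered concomitant medications". SAP 7.5.5 says: "Medications taken prior to entering the study and started while on study (i.e., concomitant) will be summarized to Week 48". SAP 7.5.2 tabulates patients receiving medications before and during each stage, with no condition on when the drug was started.

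**The concern.** The rule treats the last masked dose as if it were the end of treatment. Stage 2 then adds 96 weeks, and the sub-study a further 96. Before the anchor, a partial stop takes the latest possible day. After it, a partial stop takes the earliest possible day or is pulled back to the anchor itself. The convention therefore reverses at the point where open-label treatment begins.

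Protocol 11.10 asks for the type and timing of concomitant medication between visits, and says that "any other therapies for aniridia will be considered with special interest". Drops, lubricants, topical cyclosporine and surgery are all permitted during the study (Protocol 7.1.1). If such a treatment is recorded as stopping too early, or in the wrong stage, the tables give a reader of the open-label results a poorer account of what else was in use. A Stage 2 drug wrongly placed in Stage 1 also adds false use to the between-arm medication comparison that SAP 7.2 plans through Week 48.

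**Working it through.** The plan gives no figure on this point, so there is none to reproduce. The check applies the rules to enumerated dates.

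**Inputs.** Stage 2 is Weeks 49 to 144: 96 × 7 = 672 days. The sub-study is another 672 days. Assumptions: the last masked dose may fall on any day of a calendar year, and true stops are spread evenly over the period.

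**1. Drug carried over from Stage 1, stop in Stage 2.** Use disappears from Stage 2 only if the imputed stop is no later than the last masked dose.
- Year only: this needs a stop in the same calendar year as that dose. On average 182 days of the year remain: 182 / 672 = 27%.
- Day missing: this needs a stop in the same month. On average 14.7 days remain: 14.7 / 672 = 2.2%.
- Later year or later month: none are lost, because January 1 of a later year and the first of a later month both fall after the anchor.

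Example with last masked dose 15 Jun 2018: a true stop of 20 Oct 2018 recorded as 2018 becomes 15 Jun 2018, so Stage 2 use is lost. Recorded as Oct 2018, it becomes 1 Oct 2018 and stays in Stage 2. A true stop of 20 Oct 2019 recorded as 2019 becomes 1 Jan 2019 and also stays.

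**2. Drug started in Stage 2, start date known.** The start-date floor protects it: 0 of 679,776 enumerated combinations left Stage 2.

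**3. Drug used only in Stage 2, both dates year-only.** The floor can fail, because the start is imputed first. Take first dose 17 Mar 2017, last masked dose 15 Feb 2018, and true use June to October 2018, with both dates recorded as 2018. SAP 10.2.2.1 gives a start of 1 Jan 2018, and SAP 10.2.2.2 gives a stop of 15 Feb 2018. The drug sits wholly in Stage 1. On an even grid of Stage 2 start and stop pairs, this happens to about 10% of year-only pairs and about 0.1% when only the days are missing.

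**4. Shortening.** For Stage 2 stops in a later year, the mean difference between true and imputed stop is 159 days. Over all year-only Stage 2 stops it is 149 days. Both are about 5 months. For day-missing stops it is about 15 days.

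**5. Sub-study.** A stop known only to the year in which the sub-study begins becomes January 1 of that year, before the sub-study starts. By the arithmetic of step 1, about 27% of year-only and 2% of day-missing sub-study stops leave the sub-study. They remain in Stage 2.

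**6. Definition.** Under Protocol 7.1, a drug started years earlier and still taken is concomitant. The parenthesis in SAP 7.5.5 attaches the word to drugs started on study, but the same sentence also summarizes drugs taken before entry over the same periods, and SAP 7.5.2 counts them by use. The conflict is in the label.

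**The case against.** A reader might infer that treatments used in Stage 2 generally drop out of the tables, or that every partial stop in the crossover year is lost. The rules do not support that. The January 1 and first-of-month rules never remove a drug from Stage 2; a known later month keeps it there, and so does a known Stage 2 start. Loss needs a carried-over drug with a same-year (year-only) or same-month (day-missing) stop, or the both-dates-partial case in step 3.

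A reader might also infer that long-standing eye drops vanish from the concomitant tables because of SAP 7.5.5. SAP 7.5.2 and the rest of the 7.5.5 sentence point the other way.

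It is fair to add that complete dates are untouched, that medication use is collected at every clinic visit (Protocol 8.3.13), and that by-subject listings are planned (SAP 7.2). The Week 48 efficacy models use no medication dates (SAP 7.7), and surgery has its own rule (SAP 10.1). Nothing shows that any conclusion about ataluren turns on an imputed stop date. Choosing the latest date also has its own error, in the opposite direction.

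All of this limits the point to descriptive tables. It does not justify the anchor: a stated rule that can put open-label use in the wrong stage or visit interval still conflicts with the timing summary in Protocol 11.10.

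**Conclusion.** The point holds as a minor flaw in the medication tables. For carried-over drugs, about 27% of year-only and 2% of day-missing Stage 2 stops would lose their Stage 2 use, and a drug used only in Stage 2 can be assigned wholly to Stage 1 when both dates are year-only. Other partial stops after the masked phase remain in Stage 2 but are shortened by about 5 months or 15 days on average, and may disappear from later visit intervals or from the sub-study. These figures rest on evenly spread dates and are shares of partial dates only. The documents do not say how many dates will be partial, so the net effect on the tables is unknown and may be small. The definition of concomitant needs one wording, but no drug is shown to be omitted because of it. The primary and key secondary Week 48 analyses are unaffected.

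**What to change.** In SAP 10.2.2.2, impute a partial stop date to the latest date consistent with its known parts (month end or December 31), capped at last contact. Assign use to stages by comparison with the first open-label dose date. Where start and stop are both known only to the crossover year, state that imputation must not confine the drug to Stage 1.

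In SAP 7.5.5, replace the parenthetical with the Protocol 7.1 definition: taken from screening through the 4-week follow-up, whatever the start date. That agrees with SAP 7.5.2. A definition based on use on or after first dose would not do, because Protocol 7.1 starts at screening.

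The cost is SAP wording and a programming change. The downside is that some year-only records will overstate duration, by up to 12 months before the last-contact cap, and some drugs stopped in Stage 1 will appear to run into Stage 2. Imputed dates should be flagged in the listings so that a reader can see which records these are.

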Appendix A Schedule of Events

The types and timing of data to be recorded are summarized in Table 1 (Stage 1, double-masked period), Table 2 (Stage 2, open-label period), and Table 3 (open-label sub-study).

Table 1. Schedule of Events (Stage 1)

Protocol Activities		Screening				Double-Masked Treatment			
Day±Window	Week	-28	-4	1 ^a	1	169±28	24	337±28	48/ End of Stage 1 ^b
Visit		1		2		3			4
Informed consent		X							
Medical and ophthalmic history ^c		X							
Serum viral screen		X							
Physical exam		X		X					X
Height and weight		X		X		X			X
Vital signs		X		X		X			X
Ophthalmoscopy		X		X		X			X
Hematology, biochemistry, urinalysis		X				X			X
Serum β-HCG ^d		X		X		X			X
Study drug and diary dispensing				X		X			X
Study drug administration				X		X			X
Study drug compliance and return						X			X
Collect diary						X			X
Adverse events				X		X			X
Concomitant meds		X		X		X			X
MNREAD				X					X
████████████████████				X		X			X
Slit-lamp examination ^e				X		X			X
Slit-lamp photography				X		X			X
OCT				X		X			X
Fundus photography				X		X			X
Humphrey visual fields				X					X
BCVA (visual acuity and refraction) ^f		X		X		X			X
████████████████████				X		X			X
████████████████████				X		X			X
████████████████████ blood				X		X			X
sample for plasma PK ^g									If feasible (i.e., during surgery for glaucoma, cataracts, etc.)

Abbreviations: β -HCG, beta-human chorionic gonadotropin; BCVA, best corrected visual acuity; ETDRS, Early Treatment Diabetic Retinopathy Study; [REDACTED]; LEA, LEA Symbols Visual Acuity Test System; MNREAD, Minnesota Low Vision Reading (MNREAD) Acuity Charts; OCT, optical coherence tomography; PK, pharmacokinetic(s)

^a All study and laboratory assessments on the first day of treatment must be done prior to in-clinic administration of the first dose.

^b Open-label study drug administration will start at the end of Stage 1 (Visit 4/Week 48).

^c Should include capture of available historical values for ocular assessments included in this study, such as visual acuity, [REDACTED], etc.

^d Sample taken only for female subjects of childbearing potential.

^e Slit-lamp examination should precede [REDACTED] measurement.

^f Visual acuity and refraction will be assessed using the Early Treatment Diabetic Retinopathy Study (ETDRS) or an age-appropriate alternative (e.g., LEA).

Table 2. Schedule of Events (Stage 2)

Protocol Activities		Open-Label Treatment						End of Study)/ Early Termination ^a		Follow-Up ^b	
Day±Window	Week	505±28	72	673±28	96	841±28	120	1009±28	144	28 Days Post EOS/ET±7	148
Visit		5		6		7		8		9	
Physical exam				X				X		X	
Height and weight		X		X		X		X		X	
Vital signs		X		X		X		X		X	
Ophthalmoscopy		X		X		X		X		X	
Hematology, biochemistry, urinalysis		X		X		X		X		X	
β-HCG ^c		X		X		X		X			
Study drug and diary dispensing		X		X		X					
Study drug administration		X		X		X					
Study drug compliance and return		X		X		X		X			
Collect diary		X		X		X		X			
Adverse events		X		X		X		X		X	
Concomitant meds		X		X		X		X		X	
██████████		X		X		X		X			
MNREAD				X				X			
Slit-lamp examination ^d		X		X		X		X			
Slit-lamp photography		X		X		X		X			
OCT		X		X		X		X			
Fundus photography		X		X		X		X			
Humphrey visual field				X				X			
BCVA (visual acuity and refraction) ^e		X		X		X		X			
██████████		X		X		X		X			
██████████		X		X		X		X			
██████████		X		X		X		X			

██████████ blood sample for plasma PK^f If feasible (e.g., during surgery for glaucoma, cataracts, etc.)

Abbreviations: β-HCG, beta-human chorionic gonadotropin; BCVA, best corrected visual acuity; EOS/EOT, end of study/end of treatment; ETDRS, Early Treatment Diabetic Retinopathy Study; ██████████; LEA, LEA Symbols Visual Acuity Test System; MNREAD, Minnesota Low Vision Reading (MNREAD) Acuity Charts; OCT, optical coherence tomography; PK, pharmacokinetic(s)

^a Refer to Table 3 for the schedule of events for subjects participating in the sub-study for Visits 8-13.

^b This visit is only required for subjects not participating in the sub-study.

^c Sample taken only for female subjects of childbearing potential.

^d Slit-lamp examination should precede ██████████ measurement.

^e Visual acuity and refraction will be assessed using the Early Treatment Diabetic Retinopathy Study (ETDRS) or an age-appropriate alternative (e.g., LEA).

^f ██████████

Table 3. Schedule of Events (Open-label Sub-study)

Protocol Activities	Open-Label Treatment					End of Study/ Early Termination	Follow-Up
	144 ±28 days	168±28 days	192±28 days	216±28 days	240 ±28 days	28 Days (4 weeks) Post EOS/ET (Week 244±7days)	
Week	8	9	10	11	12	13	
Informed consent	X						
Physical exam	X						X
Height and weight	X	X	X	X	X	X	X
Vital signs	X	X	X	X	X	X	X
Ophthalmoscopy	X	X	X	X	X	X	X
Hematology, biochemistry, urinalysis	X	X	X	X	X	X	X
β-HCG ^a	X	X	X	X	X		
Study drug and diary dispensing	X	X	X	X			
Study drug administration	X	X	X	X			
Study drug compliance and return	X	X	X	X	X		
Collect diary	X	X	X	X	X		
Adverse events	X	X	X	X	X	X	X
Concomitant meds	X	X	X	X	X	X	X
████████████████████	X						
MNREAD	X	X	X	X	X		
Slit-lamp examination ^b	X						
Slit-lamp photography	X						
OCT	X						
Fundus photography	X						
Humphrey visual field	X					X	
BCVA (visual acuity and Refraction) ^c	X	X	X	X	X	X	
████████████████████	X						
████████████████████	X	X	X	X	X		
████████████████████	X						
Schedule next visit	X	X	X	X	X		

Abbreviations: β-HCG, beta-human chorionic gonadotropin; BCVA, best corrected visual acuity; EOS/EOT, end of study/end of treatment; ETDRS, Early Treatment Diabetic Retinopathy Study; ██████████; LEA, LEA Symbols Visual Acuity Test System; MNREAD; Minnesota Low Vision Reading (MNREAD) Acuity Charts; OCT, optical coherence tomography

^a Sample taken only for female subjects of childbearing potential.

^b Slit-lamp examination should precede ██████ measurement.

^c Visual acuity and refraction will be assessed using the Early Treatment Diabetic Retinopathy Study (ETDRS) or an age-appropriate alternative (e.g., LEA).
